## **Background and significance**

Premature infants are defined as those born before 37 weeks of gestation. Their growth and development require more meticulous attention and specialized care. Due to underdeveloped organs and weakened immune systems, family members often lack a comprehensive understanding of the unique needs of preterm infants within traditional medical care settings, which may lead to gaps or deficiencies in the caregiving process. The involvement and supportive role of the family are often insufficient, making it difficult to meet the complex care requirements of premature infants in the neonatal intensive care unit (NICU). Currently, the family-centered care model is widely implemented in clinical practice and has demonstrated positive outcomes in improving care quality and patient outcomes.

The care of premature infants necessitates collaborative efforts between healthcare professionals and family members. This study introduces a family-participatory care model grounded in Swanson's theory of caring. By fostering greater family involvement and initiative, caregivers can develop a deeper understanding of the infants' specific care requirements and design individualized care plans accordingly. This approach holds significant value in supporting the physical development of premature infants and preserving the psychological well-being of their families.

The comprehensive implementation of this project can deliver tailored services to premature infants and their families, more effectively addressing their specific care requirements. By adopting a more professional and individualized care approach,

premature infants can experience a greater sense of security, while the psychological stress on their families can be alleviated. The family-centered care model encourages active involvement of family members in the caregiving process. Through hands-on experience and guided practice, family members can acquire essential skills for caring for premature infants. Close collaboration between family members and healthcare professionals significantly enhances the overall effectiveness of care. Furthermore, this collaborative environment fosters stronger trust and mutual support among family members, enabling premature infants to achieve faster and more stable recovery under scientifically guided care.

Furthermore, the promotion of a family-integrated care model can enhance the professional competence and communication abilities of healthcare personnel, foster close collaboration between families and medical institutions, and encourage innovative thinking among medical staff in the care of premature infants, thereby promoting mutual development and improved outcomes. Therefore, this project not only effectively improves the health outcomes of premature infants and enhances the well-being of their families, but also contributes to the innovation of care models in nursing practices and provides a theoretical foundation for the advancement of premature infant care services.

## **The current research status and development trends**

Akturk U (2018) proposed  the establishment of a multidisciplinary care intervention team comprising nurses, physicians, and psychological counselors. Prior to the implementation of the intervention, the psychological counselor should conduct comprehensive training for the entire team. During this phase, the team would collaboratively review and clarify the theoretical foundations of Swanson's theory, essential caregiving skills, and the psychological characteristics of patients. Based on this foundational work, an effective care framework and operational mechanism can be developed, ultimately enhancing the overall quality of patient care.

Health literacy serves as a critical foundation for delivering high-quality healthcare. Improving the health literacy of patients and caregivers can enhance the

efficiency and effectiveness of care delivery. According to the World Health Organization, individual health literacy encompasses the knowledge, motivation, and skills that enable individuals to access, understand, and apply health information and services in order to promote and sustain their health .

Swanson's theory was developed by the distinguished British professor Swanson. The theoretical framework is primarily inspired by three phenomenological studies . First, it explores which types of caregiving behaviors are most beneficial for pregnant women who have experienced unsuccessful childbirth. Second, it investigates the care requirements of new parents and the corresponding caregiving behaviors exhibited by caregivers. Finally, the theory establishes a caregiving model tailored for high-risk pregnant women—such as first-time mothers, single parents, and individuals with low educational attainment or socioeconomic status. Following the implementation of the intervention, these women demonstrated a significant improvement in their ability to care for their newborns.

[name] proposed that, with regard to care behaviors, caregivers should actively acquire an understanding of the identities of the service recipients, the methods of providing effective care, and the rationale behind their ongoing service provision. Furthermore, caregivers are expected to integrate multidisciplinary knowledge, including aspects of caregiving and humanistic concern .

Currently, the Swanson theory has gained widespread popularity and demonstrated favorable outcomes in practical applications. Studies indicate that international scholars have extensively applied this theory across various domains, including maternal care for pregnant and postpartum women, rehabilitation for individuals with limb dysfunction, mental health support for those experiencing post-traumatic stress disorder, and management of patients with hypertension . However, its implementation within China remains in the early stages.

Most NICU operate in a closed format without accommodating parental presence or active involvement . Nevertheless, in such settings, nursing staff typically assume primary caregiving responsibilities, while parents remain largely excluded from the care process. Consequently, caregivers often experience heightened anxiety and

insufficient preparedness following the discharge of preterm infants, which may result in significant caregiving challenges.

FI Care  emphasizes that parents should assume the primary responsibility for caring for premature infants in the NICU and asserts that they should serve as the principal caregivers and decision-makers. Research indicates that a family-centered care approach can significantly alleviate parental stress and anxiety. The United States has developed a data collection platform to support research on family-participatory care models , offering a valuable resource for parents who are unable to visit hospitals to understand the care requirements of premature infants. This indicates that international research on family-participatory care models began earlier and was conducted on a larger scale, thereby providing both theoretical foundations and practical guidance for enhancing parental caregiving capabilities.

## **Research Topics and Technological Approaches**

### **3.1 Main topic**

The care of premature infants represents a multifaceted challenge that involves not only physical and mental health aspects but also broader socio-economic considerations. Swanson's Caring Theory is a well-established nursing framework that emphasizes the provision of comprehensive and systematic care, centered on principles such as understanding, companionship, support, empowerment, and the preservation of hope. This study seeks to investigate the application and impact of Swanson's Caring Theory within the context of family-participatory care for premature infants.

The care process is guided by the five core principles of Swanson's Theory of Caring. 1. Knowing: Provide the family with a comprehensive explanation of the preterm infant's development, potential complications, and essential care considerations to ensure they have a thorough understanding of neonatal care requirements. 2. Being with: Offer consistent emotional presence and companionship to the family within the NICU setting, aiming to alleviate feelings of anxiety and helplessness while fostering a relationship of trust. 3. Doing for: Support and guide family members in actively participating in the infant's daily care routines, including

feeding, diaper changing, and basic physical assessments. 4. Enabling: Acknowledge and validate the emotional challenges experienced by the family, provide appropriate psychological support, and assist them in accessing relevant social and professional resources. 5. Maintaining belief: Foster a sense of hope and resilience by maintaining open, positive communication and encouraging the family to remain optimistic about the infant's progress and their own capacity to cope with challenges.

The impact of family-involved care on premature infants was assessed through various indicators, including infant health outcomes such as growth and development metrics (e.g., weight, height, and head circumference), the psychological well-being of family members, objective evaluations of caregiving quality (such as accuracy and timeliness of care delivery), and family satisfaction surveys.

### **3.2 Technological Approaches**

#### **1. Family participation**

Family participation constitutes a central principle in family-centered care. It is essential to appropriately evaluate the extent of family members' involvement in daily caregiving practices, in order to ensure their rightful role and accountability in the care process and to facilitate their comprehensive understanding of the unique needs of preterm infants. This evaluation can be systematically conducted through family-administered questionnaires, observational metrics, and assessments performed by healthcare professionals.

#### **2. Communication skills**

A comprehensive understanding and continued adherence to Swanson's Caring Theory highlight the critical role of effective communication in the caregiving process. Enhancing the communication abilities of both healthcare professionals and family members, as well as engaging in thorough communication regarding the infant's needs and care procedures, contributes to the establishment of genuine trust and minimizes communication barriers throughout the care delivery.

#### **3. Emotional Empowerment**

This serves as a critical technical indicator for assessing the suitability of family members for participation in patient care, particularly in cases involving emotional

disturbances or mental health conditions within the family. It necessitates that healthcare professionals possess specialized emotional support capabilities and the ability to provide appropriate guidance. Through open and empathetic communication, medical staff should progressively adapt to the evolving needs of the patient's family.

#### 4. The correctness of care operations

The care of premature infants requires a high level of professional expertise. Errors in care procedures can easily cause serious harm to the infants. Therefore, it is very necessary to assess and record the correctness of care procedures, as well as the improvement of skills of family members during the process of learning and familiarizing themselves with the care procedures.

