#### 5. The timeliness of care

As premature infants are a high-risk group, their health conditions may change dramatically. It is very important to assess the timeliness of care, which can help detect and solve problems in the early stage. The missed visit count method can be used to statistically record the timeliness of care.

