##### 2. Intervention and Control

FICare nursing method guided by Swanson's caring theory encompasses the following five dimensions:

Understanding: A neonatologist provided a comprehensive explanation regarding the developmental progress of premature infants, potential complications, and essential aspects of nursing care to ensure the family gained a thorough understanding

of the care requirements for premature infants.

Accompaniment: Two nursing guides provided essential support to parents of newborns in the NICU, helping to alleviate the anxiety and sense of helplessness among family members and fostering a relationship of trust between the medical staff and the families.

Help: A neonatal nurse played a guiding role in facilitating parental involvement in the daily care of premature infants, which encompassed feeding guidance, introduction of complementary foods, skin care, and related aspects.

Empowerment: A psychological counselor was assigned to provide psychological counseling and guidance to new parents, offering appropriate emotional support and assisting them in accessing necessary social and professional resources.

Maintaining Confidence: A neonatologist and a nurse monitored neonatal development through outpatient visits and telephone follow-ups to encourage families to sustain their confidence in improving infant health outcomes and to support them in maintaining a positive outlook when facing challenges in caregiving.

The control group will continue to receive the traditional model of hospital care, encompassing standard medical services such as physical health monitoring and nutritional support.

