### 3. Outcome

The primary outcomes included the corrected head circumference, weight, and height of the newborns at 1 month, 3 months, and 6 months of age. Additionally, parental anxiety and depression status was assessed using the Trait Anxiety Inventory (T-AI), which measures long-term and stable anxiety tendencies, and the State Anxiety Inventory (S-AI), which evaluates current or recent anxiety states. Parental self-efficacy and satisfaction with their parenting role were assessed using the Child-Parental Self-Competence Scale (C-PSOC).

Secondary outcomes included the length of hospital stay, discharge weight, and the number of unplanned hospitalizations.

Confounding factors included fetal gender, gestational age, birth weight, duration of oxygen therapy, duration of total enteral feeding, and the duration required to

transition from full enteral feeding to full oral feeding, defined as the time from the initiation of oral feeding (when preterm infants begin to suck voluntarily and consume the first milk volume exceeding 5 mL) to the complete establishment of full oral feeding.

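### No listed outcome counts harm to infants during the index stay, although the plan names care errors as a serious hazard, and length of stay has no rule for death or transfer.

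*Combined protocol and SAP*

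**What the plan says.** All references are to the combined protocol and SAP.

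- **The hazard.** Section 3.2, item 4: "Errors in care procedures can easily cause serious harm to the infants". The same item goes on to say that "it is very necessary to assess and record the correctness of care procedures". Item 5 adds: "As premature infants are a high-risk group, their health conditions may change dramatically".
- **Who gives care.** Section 4.1, item 2, for the intervention group: "A neonatal nurse played a guiding role in facilitating parental involvement in the daily care of premature infants". Section 3.1, under the third caring principle, gives feeding, diaper changing and basic physical assessment as examples. For the comparator, "The control group will continue to receive the traditional model of hospital care"; no guided parental care is described there.
- **Care quality as an indicator.** Section 3.1 names the accuracy and timeliness of care among the things to be assessed.
- **Outcomes.** Section 4.1, item 3: "The primary outcomes included the corrected head circumference, weight, and height of the newborns at 1 month, 3 months, and 6 months of age". Parental anxiety and parenting-competence scales follow. Then: "Secondary outcomes included the length of hospital stay, discharge weight, and the number of unplanned hospitalizations". The item ends with covariates labelled as confounders, including duration of oxygen therapy and the time taken to reach feeding milestones.
- **Analysis.** Section 4.1, item 5, offers a t-test or Mann-Whitney test according to distribution. It has no rule for an infant who dies or is transferred before discharge.

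**The concern.** The plan names a risk to the infant, and its intervention changes exposure to that risk in one group only. Harm during the hospital stay is therefore something the trial needs to compare between groups, and no listed outcome does so. The trial could report better growth or lower parental anxiety with its own stated risk uncounted.

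Two listed outcomes also become ambiguous if the worst events occur. Length of stay has no definition. If days are counted to the end of the stay for whatever reason it ended, an early death or transfer gives a short stay, which reads as benefit. Growth at 1, 3 and 6 months has no value after a death, so growth results shown alone would silently describe survivors.

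**Working it through.** **Step 1. The plan's own figure.** Section 4.1, item 4, gives z-values of 1.96 and 0.84, variance 2.5, difference 1.5 and a minimum of 18 per group.

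n = 2 × (1.96 + 0.84)² × 2.5 / 1.5² = 39.2 / 2.25 = 17.42, rounded up to 18.

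The figure is reproduced, and 18 per group is used below.

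**Step 2. Does any outcome count harm in the index stay?**

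| Item in section 4.1, item 3 | Counts in-hospital harm? |
|---|---|
| Head circumference, weight, height at 1, 3, 6 months | No; needs a surviving, followed infant |
| Parental anxiety and competence scales | No; parent outcomes |
| Length of stay | No; undefined, direction ambiguous after death or transfer |
| Discharge weight | No |
| Unplanned hospitalizations | No; concerns admissions, not events within the index stay |
| Oxygen and feeding durations (labelled confounders) | No; they describe clinical course and are not event counts |

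**Step 3. How likely is any event?** The documents give no event rates, so these are assumptions. P(at least one in 18) = 1 − (1 − p)^18.

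| Assumed p | P(at least one event) |
|---|---|
| 1% | 0.165 (17%) |
| 2% | 0.305 (30%) |
| 5% | 0.603 (60%) |
| 10% | 0.850 (85%) |

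**Step 4. What would zero events show?** Exact upper limits for 0/18:

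- one-sided 95%: 1 − 0.05^(1/18) = 0.153
- two-sided 95%: 1 − 0.025^(1/18) = 0.185

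Power to detect 5% versus 20% (assumed rates) is about 27% at 18 per group. Harm can be described in this trial but not usefully tested.

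**Step 5. How far could length of stay move?**

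- *By ranks.* The SD of U at 18 versus 18 is √(18 × 18 × 37 / 12) = √999 = 31.6. Moving one infant from the shortest to the longest stay of all changes U by 18, so z moves by 18 / 31.6 = 0.57. Two deaths move it by 1.14. If death is ranked shortest, the shift favours the group in which the infant died. An early event that is not the shortest stay of all moves z by less.
- *By means.* The shift for one infant is (average stay − event day) / 18. With an assumed 30-day average and an event on day 3, it is 27 / 18 = 1.5 days. Over assumed averages of 20 to 40 days and events on day 3 to 10, it runs from 10 / 18 = 0.6 to 37 / 18 = 2.1 days.

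**The case against.** The best defence is that the plan is not silent and the expected harm is small.

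- *Correctness of care is to be recorded.* This is true of sections 3.1 and 3.2, and it rules out the inference that the plan ignores care errors. But whether a procedure was done properly is a process measure. It has no definition, assessor or analysis, and it is not carried into the outcome list. It does not count injured infants.
- *No text scores a death as a good outcome.* A reader might infer that the plan treats death or transfer as a shorter and therefore better stay. The documents do not support that. Length of stay is simply undefined, and a late death could lengthen it. The problem is a missing rule.
- *Few events are likely.* Section 4.1, item 1, requires 24 hours of stable vital signs and excludes vital-organ dysfunction, mechanical life support, surgical need and severe congenital or genetic disorders. This stands, and it is why rates of 1% and 2% belong in the range. Low rates limit what can be inferred, but they do not justify leaving events uncounted.
- *The effect on length of stay is modest.* This also stands. It is a secondary outcome, and from a null result about four deaths in one group of 18 would be needed to reach 1.96 (1.96 / 0.57 = 3.4). The rank figure applies only if the Mann-Whitney test is used.
- *Parents are guided, not left in charge.* This is correct, and section 4.3 assigns risk management and regular monitoring to the project leader. Neither passage defines any harm data to be collected.

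**Conclusion.** The gap is real and worth correcting. The plan identifies serious harm from care errors, involves parents in guided daily care in one group only, and lists no outcome that counts harm events before discharge. It could therefore conclude that the model is beneficial with that risk unreported.

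The length-of-stay problem is secondary: an early death or transfer could enter as favourable because no rule is given. Its size is 0.57 in z for one death, taking the extreme ranks and no ties. On means it is 0.6 to 2.1 days per infant under assumed stays and event days.

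The text does not show that the plan scores death as benefit, that it disregards care errors, or that the intervention is unsafe. The event rates, average stays and event days are all assumptions, and 18 per group is the plan's stated minimum. Larger groups would tighten the zero-event limits and dilute the effect of a single infant.

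**What to change.** In section 4.1, item 3:

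1. Add a descriptive secondary safety outcome, taken from the hospital record from enrolment to discharge, with the same prespecified objective definitions in both groups: death, transfer to a higher level of care, new infection, and recorded feeding-related adverse events. Attribution of an event to a care error is best left out. It needs judgement, and the documents describe no blinding of those who would make it.
2. Report the number of infants with at least one event by group, with exact confidence intervals. Make no claim of safety from zero events.
3. Define length of stay as days to discharge home alive.
4. Report transfers by group, adding days in the receiving hospital where these can be obtained at follow-up.
5. Report deaths by group beside the growth results.

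In section 4.1, item 5, state that length of stay is compared by ranks, with death ranked as the longest stay.

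The cost is slightly more record abstraction, written event definitions, and wide intervals for rare events. Receiving-hospital days need information from outside the hospital's own record, so they may be incomplete. The sample size of 18 per group and the care given are unchanged.

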#### 5. The timeliness of care

As premature infants are a high-risk group, their health conditions may change dramatically. It is very important to assess the timeliness of care, which can help detect and solve problems in the early stage. The missed visit count method can be used to statistically record the timeliness of care.

### **Research Plan, Technical Approach, Organizational Structure**

#### **4.1 Research Plan**

##### 1. Inclusion and exclusion criteria

The inclusion criteria were as follows: gestational age ranging from 28 to 36 weeks, stable vital signs for at least 24 hours, and parental accompaniment of preterm infants during hospitalization. The exclusion criteria included: preterm infants with severe congenital or genetic disorders, dysfunction of vital organs, or requiring mechanical life support; preterm infants requiring surgical intervention; and preterm infants with a birth weight below 500 grams.

